## WARD TEAM

Inclusion Criteria:

- Clinical staff working on the Medicine for the Elderly ward at St Mary's Hospital.
- Staff must be working regular shifts on the ward during study initiation and pilot phases
- Staff must have an active nhs.net account.

Exclusion Criteria:

[figure not shown]
- Ad-hoc bank/agency staff
- Permanent staff on long-term leave (e.g. sick/maternity) during the pilot

## 7. PARTICIPANT ENROLMENT

### PATIENTS & CARERS

**Figure 1** summarises the procedures for patient screening and enrolment. Screening and enrolment of patients and carers into the study will take place during a 3-month pilot phase of Isla's visual record platform on the Medicine for the Elderly ward. Screening and enrolment outcomes will be documented on the **screening/ enrolment log**. Potential participants (patients and carers) will be screened for eligibility by the patient's direct care team. Patients and their carers will be approached initially by members of the patient's direct care team; a team member will explain the purpose of the study and will provide a **patient and carer participant information sheets**.

Figure 1: patient screening and enrolment procedures

(a)If the patient gives any indication (whether verbal or non-verbal) that they do not wish to participate, they will not be enrolled - even if the personal consultee believes that the patient would have agreed to participate.

The first approach will take place following admission to Medicine for the Elderly ward when the patient is clinically stable. The direct care team will check whether the carer is happy to be contacted by the researcher, either by email or telephone, and will take the carer's contact details. The direct care team will flag all potential participants (patients and carers) to the researcher (an Imperial College Research Associate who holds a Licence to Attend with ICHT).

At least 24 hours after the first approach by the direct care team, the researcher will visit the patient on the ward to confirm study eligibility and to complete enrolment procedures. The researcher will approach the patient and ask them if they have any questions about the study and whether might be interested in participating. The researcher will offer to discuss the study with the patient, either at that time or another date/ time during the admission, until the patient is satisfied that all his/her questions have been answered fully. The participant information sheet contains visual aids to support the patient's understanding of what will happen to them during the study; the researcher will refer to these as needed. The researcher will offer the patient and the carer additional time to consider whether to participate.

If the direct care team have any concerns that a patient may lack capacity to consent to study participation, [name] or [name] will undertake and document a **Mental Capacity Assessment** before proceeding to enrolment.

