## 4. STUDY DESIGN

This protocol describes a single-centre, non-randomised, mixed-methods pilot study with embedded process evaluation. The revised UK Medical Research Council (MRC) framework for developing and evaluating complex interventions emphasises that feasibility assessment is essential to reduce key uncertainties around i) evaluation design (e.g. recruitment rate, outcomes), and ii) the intervention itself (e.g. acceptability, capacity of care team to deliver the intervention) (10). This current study will address key uncertainties relating to both the evaluation design and the visual patient record platform intervention to inform decisions around progression to a definitive trial.

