## 9. OUTCOME MEASURES

Primary outcome measure:

- Patient, carer and staff perspectives on the acceptability of video-based records

Secondary outcome measures:

- Recruitment and retention rates
- % of patient participants with videos linked to the electronic patient record
- Video view metrics
- Intervention barriers & facilitators
- Perceived impacts of video-based records on:
  - inpatient assessment & clinical decision-making
  - multi-disciplinary team communication
  - care continuity during a hospital stay
  - person-centred care during a hospital stay
- No. of videos raising cause for concern reported to the clinical lead

**Table 1** (see overleaf) provides a summary of outcomes, measures/ approaches for obtaining data, and analyses (qualitative and quantitative), corresponding to the primary and secondary study objectives. In line with standard feasibility study objectives, clinical outcomes are not examined at this early investigative phase of the project.

Table 1: Summary of outcomes, measures/approaches, and methods of analysis

Objective	Outcomes	Measures/data collection	Methods of analysis
Acceptability	Patient/carer acceptability	
 
- % of eligible participants declining enrolment & reasons for non-participation (screening/enrolment log)
 
- % of enrolled patients with ≥ 1 video linked to the EPR
 
- Semi-structured interview at or within 2 weeks of discharge
 
	Descriptive statistics
	Direct care team acceptability	
 
- Video evaluation questionnaire
 
- Semi-structured interview after the 3-month pilot
 
- No. of videos requested, attempted & submitted (video tracker)
 
	Descriptive statistics Framework analysis Descriptive statistics & Framework analysis Framework analysis
Feasibility	Patient enrolment	
 
-% of eligible participants who were enrolled into the study (screening/enrolment log)
 
- diversity of study sample (screening/enrolment log)
 
	Descriptive statistics
	Intervention barriers & facilitators	
 
- Semi-structured interviews with patients/carers
 
- Semi-structured interviews with direct care team
 
	Framework analysis Framework analysis

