## 10. DATA COLLECTION

### ***Screening/Enrolment Log***

The eligibility and enrolment status of all patients screened for the study will be documented on the **Screening/Enrolment Log**; this includes reasons for non-enrolment. This log will be kept in the study file in the Doctor's Office on the Medicine for the Elderly ward. It will be reviewed by and completed by the direct care team and the researcher during the 3-month pilot of Isla's platform.

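### The Table 1 enrolment and decline percentages come from a log of screened patients only, and no visible text checks that log against ward admissions, so incomplete screening would go unseen and enrolment among all eligible admissions may be overstated

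*Protocol*

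**What the plan says.** Four parts of the protocol bear on this.

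- **Who screens (section 7, Patients & carers).** "Potential participants (patients and carers) will be screened for eligibility by the patient's direct care team". The next step is that "The direct care team will flag all potential participants (patients and carers) to the researcher". The researcher then visits the ward, at least 24 hours after the team's first approach, to confirm eligibility and complete enrolment.
- **What the log holds (section 10, Screening/Enrolment Log).** "The eligibility and enrolment status of all patients screened for the study will be documented", with reasons for non-enrolment. The care team and the researcher both review and complete it.
- **What is reported (section 9, Table 1).** Under feasibility, the measure is the percentage "of eligible participants who were enrolled into the study". Under patient/carer acceptability, it is the percentage of eligible participants who decline, with reasons. Both name the screening/enrolment log as their source.
- **What it is for (section 4).** "This current study will address key uncertainties relating to both the evaluation design and the visual patient record platform intervention". Recruitment rate is given there as an example of an evaluation-design uncertainty, and the results are to inform progression to a definitive trial.

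Eligibility in section 6 rests on admission to the ward during the pilot, age 65 or over, frailty or pre-frailty as judged by the care team, and capacity or an available personal consultee. Having been screened is not a criterion.

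**The concern.** The label in Table 1 promises a percentage of eligible patients. The data source can supply only a percentage of patients who were screened and found eligible. The two agree if every eligible admission is screened. No visible text requires that all or consecutive admissions be screened, counts ward admissions, or reconciles the log with an admissions list.

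Gaps in screening are plausible without any fault on the ward. The first approach waits until the patient is clinically stable, and a patient who leaves before anyone screens them would not be in the log. The Sample Size paragraph describes the sample as pragmatic and chosen for diversity, so complete screening cannot be presumed.

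Two things are at stake. The enrolment percentage may look better than it was among all eligible admissions. And a team that could not find time to screen everyone is a feasibility finding in its own right, which this log would not record. The decline percentage has the same restricted base, and it informs the primary objective, acceptability. Its direction of error is not fixed: it depends on whether the patients missed would have declined more or less often than those screened.

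**Working it through.** **Figures the protocol gives.** The recruitment total reproduces: 30 patients + 30 carers + 35 staff = 95 (section 6 and Sample Size). The patient target is 30 in a 3-month pilot, or 30/3 = 10 per month. The protocol states no expected enrolment percentage, number of admissions, number of eligible patients or screening coverage, so there is no enrolment figure to reproduce.

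**Formula.** Let n be the number enrolled, E the eligible patients in the log, and T all eligible admissions during the pilot. Coverage is c = E/T.

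- Log percentage: n/E.
- Percentage of all eligible admissions: n/T = c × n/E.
- Ratio of the first to the second: 1/c.

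The ratio depends only on coverage. It is the same whether patients are missed at random or selectively.

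**Illustration.** Assume the target is met (n = 30) and the log holds E = 50 eligible patients, so the log percentage is 30/50 = 60.0%.

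| Assumed coverage c | T = 50/c | 30/T | Factor 1/c |
|---|---|---|---|
| 100% | 50 | 60.0% | 1.00 |
| 90% | 55.6 | 54.0% | 1.11 |
| 75% | 66.7 | 45.0% | 1.33 |
| 50% | 100 | 30.0% | 2.00 |

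**Range over E at 50% coverage.**

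- E = 40: 75% in the log, 37.5% of all eligible admissions.
- E = 60: 50% in the log, 25.0% of all eligible admissions.
- E = 75: 40% in the log, 20.0% of all eligible admissions.

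**What does not change.** Recruitment per month is n divided by 3 months. Neither E nor T enters it, so it stays at 10 per month in every scenario where the target is met.

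**The case against.** **The gap may be closed in Figure 1.** Section 7 says that figure summarises screening and enrolment, and a rule to screen all admissions could sit there or on the log form. Neither is shown in the text reviewed. This stands as a limit on the point, and Figure 1 should be checked first.

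**A reader might infer that staff choose whom to screen.** The documents do not say so. Section 7 says that potential participants will be screened and that all of them will be flagged. The staff opt-out in the Ward Team part of section 7 covers recording or appearing in videos and joining the evaluation; it does not mention screening. The researcher also reviews and completes the log. That is a real safeguard over its content, but not a check on who never entered it.

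**A reader might infer that a later trial would fall short by 1/c.** That follows only if the later trial applies the log percentage to all its eligible patients and repeats the same incomplete coverage. If unscreened patients would enrol as readily as screened ones, a later trial with full screening could expect the log percentage. Recruitment per month is also available for planning.

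**A reader might want enrolled/admitted as the planning figure.** Its denominator includes ineligible patients, such as those who are not frail or pre-frail and those lacking capacity with no consultee. Its numerator is aimed at a target of 30, so on a busy ward it partly reflects the target.

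**The count could be left to the analysis plan or report.** Nothing in the protocol prevents that. But an analysis based on the log alone cannot recover coverage, because the missing information lies outside the log. Settling the data source in the protocol is the safer course.

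**Conclusion.** The point holds in a limited form. Both Table 1 percentages rest on screened patients, and no visible text ties the log to ward admissions. If eligible admissions go unscreened, the percentage enrolled may overstate enrolment among all eligible admissions by 1/coverage: 1.11, 1.33 or 2.00 at coverages of 90%, 75% or 50%. Those coverages are assumptions. The actual size cannot be worked out from the protocol, and it is zero under full screening. The firm conclusion is that the design as written could not tell full from partial screening. The text does not support saying that the rate is overstated, or that the team screens selectively. For a descriptive single-ward study this is a cheap improvement to how recruitment is measured; it does not threaten the primary outcome.

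**What to change.** In section 10, add that at the end of the pilot the number of admissions to the ward aged 65 or over will be taken from the electronic patient record already in use there and reconciled with the screening/enrolment log. Report one flow table: admitted, screened, eligible, approached, enrolled.

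In Table 1:

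- Show screened/admitted as screening coverage beside the percentages enrolled and declining. It is coverage of admissions in the age range, and matches c above only if eligible patients were as likely to be screened as the others.
- Label both percentages as being among screened-and-eligible patients.
- Enrolled/admitted may be shown as a lower bound on enrolment among eligible admissions, but not as the sole planning figure.

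If Figure 1 already requires every admission to be screened, repeat that rule in the text of section 7; the reconciliation then serves to confirm it.

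The cost is one count, a short reconciliation task and possibly a less favourable recruitment figure. No participant procedure changes.

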### ***Enrolment of patients with capacity to consent***

If, after consideration of information about the study, the patient wishes to participate and has capacity to make that decision, the researcher will ask the patient to sign the **consent form for patients with capacity**. As part of the consent process, the patient will be asked to consider their ongoing study participation in the eventuality that they lose capacity to consent during the study (e.g. the develop confusion/delirium); the researcher will ask whether they would like to remain in the study, and whether they would still like their data to be used in the study.

### ***Enrolment of carers***

Patients' family members/ informal carers will be invited to participate as interviewees. The patient will be asked to identify a family member/ informal carer (unpaid) who provides the patient with assistance in their daily activities. If the patient's family member/ carer is available at the time the researcher visits the ward, they can be included in the discussions about the study and consent to will be sought at the same time as the patient. If the carer is not available on the ward at the time of the researcher's visit, the researcher will contact the carer by telephone. The researcher will offer to discuss the study with the family member/ carer, either at that time or another date/ time, until the family member/ carer is satisfied that all his/her questions have been answered fully. The researcher will offer the family member/ carer additional time to consider whether to participate. If the family member/ carer wishes to participate, they will be asked to provide consent, by signing a printed carer consent form or by completing the electronic carer consent form; a link to this will be sent to the carer via email or SMS.

## ***Enrolment of patients lacking capacity to consent***

If, prior to enrolment, a potential participant is assessed as not having capacity to make the decision about taking part in the study, the researcher will still provide the potential participant with study information according to their capacity of understanding and using the photographs in the information sheet as visual aids, if needed.

Reasonable steps will be taken to identify a personal consultee, in line with the requirements of section 32(3) of the *Mental Capacity Act 2005* and the Department of Health's *Guidance on nominating a consultee for research involving adults who lack capacity to consent* (2008). A personal consultee will be identified by the patient's direct care team. The personal consultee could be a family member, carer (unpaid) or friend, who knows the patient well and assists them with their daily activities, including making decisions about their welfare; this person may already be acting under a Lasting Power of Attorney, but this is not a pre-requisite.

If no appropriate person can be identified who is willing to act as a personal consultee, the patient will be excluded from the study. Note: *nominated* consultees will not be appointed for the purposes of this study; members of the patient's direct care team on the Medicine for the Elderly ward cannot be nominated as consultees because the direct care team are involved with the study.

The initial contact with the potential consultee will be made by the patient's direct care team. The direct care team will outline the purpose of the study and the role of a consultee, emphasising to the potential consultee that he/she is not obliged to undertake this role. The direct care team will ask the potential consultee if the researcher may contact them directly to provide further information about the study; this could be over the telephone or face-to-face on the ward. The researcher will provide full verbal and written information about the study (**consultee information sheet**). The consultee will be asked to consider the patient's likely wishes and feelings about taking part. The researcher will offer the consultee additional time to consider this before communicating the patient's likely wishes and feelings about study participation to the researcher. The researcher will make it clear to the consultee that they are not being asked to provide their personal views on study participation, nor are they being asked to consent to the study on the patient's behalf. A decision to recruit or exclude the patient will be made by the researcher in line with the consultee's advice and any previous relevant statements or wishes communicated by the patient, whether verbal or non-verbal. Consultee advice will be recorded on a **printed consultee declaration form** or an **electronic consultee declaration form**. If the consultee advises that the patient would not have wanted to take part, the researcher will abide by this. If a consultee is not available or declines to offer advice about the patient's wishes, the patient will be excluded from the study.

## ***Patients who lose capacity during the study***

During the initial consent process, patients will be asked to consider whether they would want data already collected about them that is in an identifiable form (e.g. video-recordings) to be used in the study in the event that they lose capacity (e.g. if they develop confusion/delirium as a result of their illness). The research team will act in accordance with the patient's wishes. The Study Information Sheet includes a clear statement regarding retention and use of identifiable data following loss of capacity.

During the initial consent process the patient will also be asked to consider whether they would want to continue to be included in the study in the event that they lose capacity. During the study, capacity of participants will be monitored by the direct care team. During the study, capacity of participants will be monitored by the direct care team and there will be regular communication between the clinical lead and the researchers about capacity concerns. If loss of capacity occurs a personal consultee would be sought to advise on whether the patient should continue to be included in the study. The consultees' advice will be documented on a **consultee declaration form**.

### ***Patients who regain capacity during the study***

If a patient who lacked capacity to consent to study participation subsequently regains capacity during the study, the researcher will approach the participant to explain what has happened to the participant as part of the study so far, and to seek ongoing consent. The researcher will provide the participant with a **recovered capacity participant information sheet**. The researcher will also provide the patient with verbal information about the study, including what has already happened to the patient as part of the study. Consent for continued participation will be documented on the **recovered capacity consent form**. Should the participant wish to withdraw from the study, the researcher will inform the patient about how their data will be handled depending on the stage at which the patient withdraws from the study:

- If no video-recordings have been taken, the researcher will communicate to the direct care team that the patient has withdrawn consent for study participation and no recordings should be taken. The patient's data will not be included in the study.
- If video-recordings have already been taken, the patient will be advised that these recordings will continue to form part of the patient's electronic health record and they will be available for review by the direct care team only for the purposes of patient care. However, the patient can request that their data remains in the study or is removed. The patient's wishes regarding the handling of their study data will be documented on the recovered capacity consent form.

### **WARD TEAM**

There will be a 4-week staff engagement and enrolment phase for the direct care team on the Medicine for the Elderly ward at the beginning of the study. All clinical staff working on the Medicine for the Elderly ward will receive verbal and written information about the study from the research team during twice-weekly drop-in sessions and routinely scheduled team meetings (**staff study information sheet**). Staff will be informed about:

- the aims of the study
- study eligibility for patients and their family members/carers
- the purpose of the video-recordings
- permitted uses of the video-recordings
- access to the video footage
- governance measures and mechanisms for ensuring patient and staff privacy and confidentiality
- what staff can expect should they choose to participate in the evaluation of the video-recording pilot.

Staff will be reassured that they can choose not to be involved in recording or appearing in patient videos. They can also choose not to participate in the evaluation of the video-recording pilot. Staff will have the opportunity to ask questions and have them answered fully by the clinical lead for the study and/or the researcher. Staff who are willing to participate in the evaluation of the video-recording initiative will be asked to sign a **ward staff consent form**.

## WITHDRAWAL CRITERIA

Participants can request to be withdrawn from the study at any time.

If a patient who lacks capacity gives any indication that he/she objects to study participation (whether verbally or non-verbally), the researcher and the personal consultee will discuss whether it would be in the patient's best interests to withdraw them from the study.

Participant withdrawal should be documented in the Screening/Enrolment Log.

